Safety and Efficacy of Trim II for Non- invasive Lipolysis and Circumference Reduction of Abdomen

NCT05398159

Last Updated Jun 3 2022

I N M O D E

Safety and Efficacy of Trim II for Non-invasive Lipolysis and Circumference Reduction of Abdomen.

Protocol No: DO609924A SIRB ID: 8659

Rev. Date: Jun 3 2022

Study Name: Safety and Efficacy of Trim II for Non-invasive Lipolysis and Circumference Reduction of Abdomen.

Protocol No.: DO609924A

Sponsor: InMode Ltd.
[name]
[name]
[name]
[contact]

I N M O D E

Safety and Efficacy of Trim II for Non-invasive Lipolysis and Circumference Reduction of Abdomen.

[figure not shown]
Protocol No: DO609924A SIRB ID: 8659

Rev. Date: Jun 3 2022

Approvals:

Revision Log:

Revision #	Date	Modification
A	January 2021	First Release
B	June 2022	

I N M O D E

Safety and Efficacy of Trim II for Non-invasive Lipolysis and Circumference Reduction of Abdomen.

Protocol No: DO609924A SIRB ID: 8659

Rev. Date: Jun 3 2022

1. Protocol Synopsis

Study Title	Safety and Efficacy of Trim II for Non-invasive Lipolysis and Circumference Reduction of Abdomen.
Protocol No	DO609924A
Sponsor	InMode Ltd.
Investigational Product	Trim II hands free device.
Study Design	Prospective, open label clinical study.
Principle Investigator and Study Site	Site 01: Site 02: Site 03: Site 04: Site 05:
Patient Population and Sample Size	At least 70 female and male subjects, from 5 investigational sites, aged 18-70 seeking non-invasive lipolysis and circumference reduction of abdomen will be enrolled.
Study Duration	Eligible subjects will receive 3 bi-weekly treatments (once in 2 weeks) with Trim II hands-free applicator belt according to the study protocol. Trim II hands-free applicator composed of 4 units applied to the abdominal area, using a single-use belt. Each treatment duration will be 45-60 minutes. Study duration for each subject is approximately 6 months (including screening, 3 treatments and 2 follow-up visits at 1 and 3 months post last treatment). Histological samples will be taken from treated area of 8-10 subjects (in total) at baseline and at 3 months follow-up visit. Overall study duration will be approximately 12 months, depending on the subject recruitment rate.

I N M O D E

Safety and Efficacy of Trim II for Non-invasive Lipolysis and Circumference Reduction of Abdomen.

Protocol No: DO609924A SIRB ID: 8659

Rev. Date: Jun 3 2022

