6.1 Primary Endpoints

- Efficacy of the Trim II treatment for lipolysis and abdominal circumference reduction.
Evaluation of change in abdomen circumference using tape measurements in cm at the 3 months follow-up visit comparing to baseline.
Success criteria: Statistically significant reduction in abdominal circumference tape measurements at the 3 months follow-up visit compared to baseline.
* The primary effectiveness endpoint will be calculated based on those patients whose weight remains stable during the study period. A subject is defined as having maintained her weight during the treatment period if it remained within $\pm 3\%$ (inclusive) of baseline for the respective period.

 I N M O D E	Safety and Efficacy of Trim II for Non-invasive Lipolysis and Circumference Reduction of Abdomen.	
	Protocol No: DO609924A SIRB ID: 8659	Rev. Date: Jun 3 2022

- Safety of the Trim II treatment for lipolysis and abdominal circumference reduction. The occurrence of adverse events will be followed throughout the whole study. Observation, assessment and recording of potential reactions by the investigator. Evaluations will be done immediately after each treatment and at the follow-up visits. The frequency, severity and causality of reactions will be recorded.

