Appendix 4.0: Circumference Measurements

The following steps are necessary to achieve consistent measurements:

- The measurement tape should be parallel to the floor during the measurement
- Prior to circumference measurement, mark the area to be treated in order to perform the measurements within the defined area for treatment. The area to be measured must be at height that includes the area to be treated.
- Baseline measurement should be taken at the level of the widest part of area (most protruding convexity) – horizontal midline. This height level should be recorded for follow up assessments. Two additional measurements will be taken at 2 inches/5cm above this baseline and 2 inches/5 cm below it.
- The consecutive measurements should be performed at the same height recorded at enrollment. In order to assure that measuring tape is parallel to the floor, several reference points should be marked around the treatment area and the measuring tape should be placed such that it is aligned with them.
- The tape should be placed under the reference points in order to maintain repetitive height of the measurement
- The measurement device should be placed at a constant tension to achieve an exact measurement of the circumference
- The same trained evaluator will preferably perform the circumference measurement to avoid bias in results. In case that evaluator is not available, another trained person will perform the procedure.

The circumference measurement:

- Position the subject next to a fixed height measuring device. Such a device could be a wooden/metal measurement stick, fixed perpendicular to the floor.
- Alternatively, a medical height measuring device will be employed.
- The height reference line should be at the widest part of the marked treatment area (horizontal mid-line).
- This height should be kept as the reference in the follow up throughout all measurements of the same treatment area.
- In order to ensure a reproducible posture, position the subject as close as possible to the measurement stick.
- Arms will be crossed over the chest with hands placed in the opposite axillae. The head will be held up with eyes level and looking straight ahead.

I N M O D E

Safety and Efficacy of Trim II for Non-invasive Lipolysis and Circumference Reduction of Abdomen.

Protocol No: DO609924A SIRB ID: 8659

Rev. Date: Jun 3 2022

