- Have the subject rotate slowly to produce the height reference line. This line should be marked on the skin as the subject rotates. Make sure that the height reference points cover the entire length of the circumference, at front, back and two sides.
- In the subject file, record the height of the horizontal mid-line of the treatment area (the distance from the floor). This will enable the operator to re-measure the subject at the same height in the follow up visits for the evaluation of the change in the circumference.
- Place the measurement tape at the widest part of the marked area. The measurement tape should be placed below the reference line.
- Record the measured circumference in the subject file
- Measure circumference at 2 inches/5 cm above the horizontal midsection of the marked treatment area
- Measure circumference at 2 inches/5 cm below the horizontal midsection of the marked treatment area.

I N M O D E

Safety and Efficacy of Trim II for Non-invasive Lipolysis and Circumference Reduction of Abdomen.

Protocol No: DO609924A SIRB ID: 8659

Rev. Date: Jun 3 2022

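### Appendix 4.0 has no step that keeps earlier circumference readings from the unblinded evaluator who takes the sole primary efficacy measurement

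*Combined protocol and SAP*

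**What the plan says.** The Protocol Synopsis describes a "Prospective, open label clinical study", and every subject is treated. Section 6.1 makes the change in tape circumference from baseline to 3 months the only primary efficacy endpoint; the other primary endpoint is safety. The success criterion is "Statistically significant reduction in abdominal circumference tape measurements at the 3 months follow-up visit compared to baseline", with no minimum in centimetres.

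Appendix 4.0 sets out the measurement. The distance of the midline from the floor is entered in the subject file, and "This will enable the operator to re-measure the subject at the same height in the follow up visits". The next steps include "Record the measured circumference in the subject file". On personnel it says: "The same trained evaluator will preferably perform the circumference measurement to avoid bias in results"; another trained person may step in if that evaluator is unavailable. On technique it asks for the recorded height, marked reference points, a level tape, a fixed posture and arm position, and "The measurement device should be placed at a constant tension to achieve an exact measurement of the circumference". It gives no means of setting or checking that tension.

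Blinded assessment is specified only for the photographs, a secondary endpoint (Section 6.2). No section blinds the tape evaluator, withholds earlier readings, or asks for an independent second reading.

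**The concern.** The height needed for each follow-up reading is kept in the same file as the values that the new reading will be compared with. The person holding the tape knows that the subject has been treated, knows which visit it is, and has probably taken the earlier readings. Tape tension is left to judgement, so a known earlier value can influence the next one without any intent.

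In a controlled trial with blinded measurement, such a shift would fall on both arms and largely cancel. Here there is no second arm. Any average downward shift at 3 months goes straight into the estimated reduction, and the success criterion asks only that the reduction be statistically significant.

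**Working it through.** **Where the information sits.** Under Section 8, circumference is taken at baseline, before the second and third treatments, at 1 month and at 3 months. By the 3-month visit there are therefore four earlier sets. If all three levels in Appendix 4.0 (midline, 5 cm above, 5 cm below) are taken each time, that is 4 × 3 = 12 earlier readings. Appendix 4.0 sends these and the reference height to the same place and describes no separation between them.

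**What the existing rules cover.** Height, marks, level tape, posture and training reduce random variation and differences between evaluators. Preferring one evaluator also removes differences between evaluators. None of these acts on one evaluator's knowledge of earlier values, and using the same evaluator makes recall more likely.

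**How little bias would matter.** The plan gives no SD, effect size or power, so there is no figure of its own to reproduce. What follows is an illustration.

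Inputs from the plan:
- Paired t-test, two-sided 0.05 (Section 14.2).
- At least 70 completers (Section 7.2).
- Primary analysis limited to subjects whose weight stays within 3% of baseline (Section 6.1), so the analysed number may be lower.

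Assumed, not in the plan:
- SD of the change: 2, 3 or 4 cm.
- Average downward reading bias b from any cause: 0.25 or 0.5 cm.
- A weight-stable set of 50 as the smaller case.
- True change: zero.

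Formulas:
- Smallest significant mean reduction = t(0.975, n−1) × SD / √n.
- Chance of a false significant reduction = upper tail beyond t(0.975, n−1) of a noncentral t with n−1 degrees of freedom and noncentrality b × √n / SD.

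For n = 70, t = 1.995 and √70 = 8.367. With SD 2, the smallest significant reduction is 1.995 × 2 / 8.367 = 0.48 cm. With b = 0.5 the noncentrality is 0.5 × 8.367 / 2 = 2.09, which gives 0.541.

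| n | Bias (cm) | Quantity | SD 2 | SD 3 | SD 4 |
|---|---|---|---|---|---|
| 70 | – | Smallest significant reduction (cm) | 0.48 | 0.72 | 0.95 |
| 70 | 0 | False significant reduction | 2.5% | 2.5% | 2.5% |
| 70 | 0.25 | False significant reduction | 18% | 10% | 7% |
| 70 | 0.5 | False significant reduction | 54% | 28% | 18% |
| 50 | – | Smallest significant reduction (cm) | 0.57 | 0.85 | 1.14 |
| 50 | 0.5 | False significant reduction | 41% | 21% | 14% |

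The table shows how sensitive the success criterion is to a systematic shift of any origin. It does not show how much of such a shift comes from seeing earlier readings, or how much concealment would remove. Neither can be computed from the plan.

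**The case against.** The strongest reply is that the documents do not show the evaluator reading old values. Appendix 4.0 says that the recorded height makes re-measurement possible; it does not say who looks it up. Section 11.1 specifies paper case report forms, but no form layout is given, so visit-specific sheets may already be in use. A reader might infer that the evaluator has to open the file and has the baseline value in hand. The documents do not go that far. What stands is that the procedure leads to the file holding the earlier values and contains no step to keep them out of sight.

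A second reply is that hiding earlier values would not blind anyone. The evaluator would still know that the subject is treated and which visit it is, and might remember the figures. The baseline reading would also be unaffected. This is correct: concealment reduces one source of bias and does not prevent observer bias.

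Third, a reader might conclude that the primary measurement is wholly unprotected. It is not. The standardisation rules are real safeguards on technique; the gap is that they do not cover knowledge of earlier values.

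Fourth, the direction is not certain. A visible earlier value could also pull a reading towards itself and understate a change. Only the downward case threatens the false-positive rate.

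Finally, the larger weaknesses are the single arm and a success criterion without a minimum size. This point does not cure them. That limits what the change achieves, but is no reason to leave an inexpensive gap open.

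**Conclusion.** The point holds as a gap in the measurement procedure for the sole primary efficacy endpoint. Appendix 4.0 keeps the height needed at follow-up and the earlier circumferences in the same file, prefers the same unblinded evaluator, and does not withhold earlier readings.

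Its size is not known. Under the assumed SDs, a 0.5 cm bias from any cause would raise the false-success rate from 2.5% to between 18% and 54% with 70 subjects, or between 14% and 41% with 50. A reader might take these as the harm done by seeing the file. They are not: they describe the total effect of an assumed bias, and the part due to visible earlier values cannot be separated out. The recommendation rests on low cost and a plausible benefit, not on a measured effect.

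**What to change.** In Appendix 4.0, state that:
- the reference height and landmarks are kept on a card that carries no circumference values;
- each visit's circumferences are recorded on that visit's own sheet;
- the evaluator is given the card and a blank sheet, and writes down the new readings before consulting any earlier ones.

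Because the case report forms are on paper, this takes a small change of page layout and a few sentences in Appendix 4.0. It alters no endpoint, test, sample size or treatment step, and needs no extra staff if sites apply the order of steps themselves.

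There are two costs. Gross recording errors would be caught just after the reading instead of during it; comparing with the earlier sheet once the new values are written down deals with this. Adherence would also depend on site discipline, since no second person enforces the order. A duplicate reading by a trained person without access to earlier values would go further, but would need staff time.

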Appendix 5.0: Scales

Subject Satisfaction Questionnaire

Satisfaction Rate	Score
Very Satisfied	+2
Satisfied	+1
Indifferent	0
Disappointed	-1
Very Disappointed	-2

Subject Therapy Comfort Questionnaire

Comfort Rate	Score
Very Comfortable	+2
Comfortable	+1
Indifferent	0
Uncomfortable	-1
Pain	-2

I N M O D E

Safety and Efficacy of Trim II for Non-invasive Lipolysis and Circumference Reduction of Abdomen.

Protocol No: DO609924A SIRB ID: 8659

Rev. Date: Jun 3 2022

Appendix 6.0: Calliper measurements

- Take two measurements next to the belly button from both sides. If measurements are not the same, record the average
- Pull out the fold of skin with the underlying layer of fat
- Place the jaws of the caliper on the pulled skinfold
- Release the trigger of the caliper so the entire force of the jaws is on the skinfold
- Keep holding firmly the fold of skin with the fingers so that the caliper is measuring just the thickness of the fold of skin
- When the caliper is placed on the skinfold it may move a little and slow down after a few seconds, then the measurement should be taken.
- Note the reading on the scale before releasing any pressure off the calipers.
- Maintain consistency with regards to type of caliper used, landmark site measured
